11.2 Baseline Values

Unless otherwise noted, baseline is defined as the last non missing value recorded before the first dose of test article. Unscheduled visits will be used in the determination of baseline values, when applicable.

For microbiologic analysis, see Section 10.3.1 for determination of the baseline sputum sample.

11.3 Adjustments for Covariates

The model for the primary efficacy and some secondary efficacy analyses will include adjustments for randomization stratification factor:

- Prior treatment of NTM caused by MABC at baseline status (received prior antibiotic treatment for NTM vs did not receive prior treatment for NTM)

If the sample size is too small in one of the randomization stratification subgroups such that an adjusted analyses cannot be performed, unadjusted analyses will be used

11.4 Handling of Dropouts or Missing Data

Data imputation methods for the primary endpoint and other analyses for the primary endpoint are described in Section 11.1.

No imputations will be made for missing values for secondary endpoints. Summaries for these endpoints will be based on observed data only.

11.5 Interim Analysis and Data Monitoring

No interim analyses or data monitoring committee are planned for this study.

11.6 Examination of Subgroups

Subgroup analyses by prior treatment for NTM or baseline microbiological characteristics (e.g., MIC values) may be conducted if subgroup sample sizes are sufficient. This will be predetermined prior to database lock.

11.7 Multiple Comparison/Multiplicity

As the study is exploratory with respect to efficacy, no adjustments for multiplicity will be made in this study.

11.8 Multicenter Studies

This is multicenter study, with approximately 20 centers in the US participating. Approximately 75 subjects will be randomly assigned, leading to approximately 4 subjects per center.

The expected low number of subjects at some centers does not allow center to be included as a covariate in the statistical model.

12. METHODS OF EFFICACY ANALYSIS

12.1 Primary Efficacy Analyses

The study is exploratory with respect to efficacy determination. The study is designed to provide an initial assessment of efficacy rather than test a specific hypothesis. Efficacy will be evaluated based on endpoints defined by subject-reported NTM symptoms, subject-reported outcomes and quality of life measures, and microbiologic assessment. Nominal p-values will be provided as descriptive statistics.

12.1.1 Primary Efficacy Endpoint

The primary efficacy endpoint of clinical response at the Day 84 visit is defined in two ways as noted in Section 10.1. For Definition 1, clinical response is defined as the improvement in severity of at least 50% of symptoms on the NTM Symptom Assessment Questionnaire that were present at baseline at the Day 84 visit and for Definition 2 clinical response is defined as the improvement in severity of at least 50% of symptoms on the NTM Symptom Assessment Questionnaire that were present at baseline at the Day 84 visit and no deterioration in severity of any symptoms present at baseline. The NTM Symptom Assessment Questionnaire has 12 symptoms listed, however subjects may not be experiencing all symptoms at baseline. Therefore, the number of symptoms each subject has scored at least Mild severity at baseline will be counted and will serve as the denominator for this definition of improvement in severity of at least 50% of symptoms. For example, a subject with 6 symptoms scoring at least Mild severity at baseline would then be considered a responder in this analysis if they experienced improvement on at least 3 symptoms. A subject with 7 symptoms scoring at least Mild at baseline would require improvement on at least 4 symptoms. Symptoms which were not

present at baseline, or which increased in severity are not considered in Definition 1 of clinical response. For Definition 2, if any symptom present at baseline (i.e., not absent) worsens in severity at the Day 84 visit, the subject would be considered a non-responder. Symptoms which were not present at baseline are not considered in Definition 2 of clinical response. Clinical response (both definitions) will be dependent on the presence of intercurrent events (ICEs) as defined in [Section 11.1.2](#). Subjects who discontinued from the trial early or who had a missing Day 84 assessment for some other reasons will be considered non responders in this analysis.

12.1.2 Estimand Framework for the Primary Efficacy Endpoint

In general, clinical response (both definitions) will use both a treatment and composite policy strategy for handling intercurrent events. Subjects who receive alternative antibiotic therapy for treatment of the NTM infection, withdraw from study treatment early, and/or die before reaching Day 84 will be considered as not achieving clinical response. Subjects with missing data at the Day 84 assessment will also be considered as not achieving clinical response.

As detailed in the ICH E9 (R1) addendum, the following 5 attributes will define the estimand framework for the primary endpoint (both definitions) and sensitivity analyses around the primary endpoint (both definitions). The primary estimand combines responses as assessed with a composite variable strategy for handling ICEs.

- Treatment condition: administration of omadacycline or placebo
- Population: ITT analysis set
- Endpoint: clinical response at Day 84
- Intercurrent events: ICEs are defined below.
- Population-level summary: between treatment group difference expressed in terms of an odds ratio

The following ICEs will be defined for the primary estimand and analysis:

- ICE-1: Subjects receiving alternative antibiotic therapy for NTM (not including chronic macrolides). This includes subjects who prematurely discontinue test article for any reason, including an adverse event, and receive alternative antibiotic therapy for NTM. Subjects with this ICE will be considered non-responders regardless of their Day 84 assessment for the primary analysis (Composite strategy).
- ICE-2: Subjects receiving chronic macrolides (starting prior to first dose of study drug). The Day 84 value for clinical response will be used regardless of the occurrence of this ICE (Treatment policy)
- ICE-3: Subjects who died prior to Day 84. Subjects with this ICE will be considered a non-responder for the primary analysis. (Composite strategy)
- ICE-4: Subjects who discontinue test article for any reason and do not receive an alternative antibiotic for NTM. Subjects with this ICE will be considered non-responders (Composite strategy).

Analyses will be conducted for both definitions of the primary endpoint. The number and percentage of subjects with a clinical response and without a clinical response will be presented by treatment group for the ITT analysis set. Exact 2-sided 95% CIs for the point estimates of the clinical response rates in each treatment group will be determined using the Clopper-Pearson method. The odds ratio (OR) (Omadacycline relative to Placebo) and p-value will be calculated using Cochran-Mantel Haenszel (CMH) test, stratified by prior antibiotic use. If the sample size is too small in one of the randomization stratification subgroups such that an adjusted analysis cannot be performed, an unadjusted analysis (chi-squared or Fisher's exact test) will be used.

12.1.3 Other Analyses for the Primary Efficacy Endpoint

The analyses described below will be performed for both definitions of the primary efficacy endpoint.

The primary analysis will be repeated for the PP analysis set.

A sensitivity analysis will also be done using the treatment policy for ICE-1 in the ITT analysis set. The Day 84 visit value for clinical response will be used regardless of subjects receiving alternative antibiotic therapy for NTM (not including chronic macrolides).

A subgroup analysis by the randomization stratification factor levels for the primary endpoint will also be conducted.

Clinical response Definitions 1 and 2 will also be analyzed at the Day 28 and Day 56 visits.

12.2 Secondary Efficacy Analyses

Secondary efficacy endpoints will be presented as collected. Missing data will not be imputed and no adjustment for ICEs will be performed. All secondary efficacy endpoints will be analyzed using the ITT analysis set. All secondary efficacy endpoints will be summarized using descriptive statistics at each scheduled time point by treatment group as described in [Section 6](#).

The Day 84 visit time point will be presented with data as collected. The Day 84/EOT visit timepoint will include subjects who end treatment on Day 84 as well as subjects who prematurely discontinue treatment.

Secondary endpoints, where appropriate, will be analyzed using an analysis of covariance (ANCOVA) model at each visit which will include the change from baseline as the dependent variable and randomized treatment group and stratification factor (prior antibiotic treatment for MABC NTM) as fixed factors and corresponding baseline score as a covariate. Model estimated least squares (LS) means, their SDs, and 95% CIs will be presented. The difference in LS means, SDs, 95% CIs, and a p-value testing the difference between treatment group LS means will be provided.

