12.5.2.2 Microbiological Response

The number and percentage of subjects with a decrease in the mycobacterial load will be determined by treatment group at Day 84 in the ITT Analysis Set. Exact 2-sided 95% CIs for the point estimate of the percentage of subjects of subjects with a decrease in mycobacterial load in each treatment group will be determined using the Clopper-Pearson method. The odds ratio (omadacycline relative to placebo) and p-value will be calculated using Cochran-Mantel-Haenszel test, stratified by prior antibiotic use.

Kaplan-Meier methods will be utilized to determine the time to growth in liquid media only and time to first negative sputum culture in the ITT Analysis Set. Time to growth in liquid medium only will be defined as the number of days from the date of test article administration to the date of the first assessment where growth is detected in liquid medium only. Time to first negative sputum culture is defined as the number of days from the date of test article administration to the date of the first negative sputum culture. Subjects who died, withdrew, or took alternative antibiotic therapy for treatment of the NTM infection prior to growth in liquid medium only or negative sputum will be censored at the date of the death, study withdrawal, or the start date of the alternative antibiotic therapy respectively. The median, 25th and 75th percentile for time to growth in liquid media and time to first negative sputum culture will be provided with 2-sided 95% CIs. A p-value will be determined using a log-rank test.

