5. DETERMINATION OF SAMPLE SIZE

As the study is exploratory with respect to determination of efficacy, the sample size determination is provided to better ensure sufficient subjects are enrolled to provide an initial assessment of efficacy rather than test a specific hypothesis. With a randomization ratio of 1.5:1, a sample size of 75 subjects (45 omadacycline and 30 placebo) will provide approximately 80% power to detect an absolute treatment difference of 30% in clinical response rate at Day 84, based on clinical response rates of 15% and 45% in the placebo and omadacycline treatment groups respectively, using a Mantel-Haenszel test with 2-sided alpha level of .05.

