6. GENERAL ANALYSIS CONSIDERATIONS

The statistical analyses will be reported using summary tables, listings, and figures (TLFs). The International Council for Harmonisation of Technical Requirements for Pharmaceuticals for Human Use (ICH) numbering convention will be used for all TLFs. Unless otherwise noted, all p-values will be 2-sided. No adjustments for multiplicity will be made in this study, and any p-values presented are not testing pre-specified inferential hypotheses.

Continuous variables will be summarized by presenting the number of observations, means, SDs, medians, minimums, and maximums. Other summaries (e.g., quartiles, 5%, 95% CIs) may be used as appropriate.

Categorical variables will be summarized by presenting counts and percentages of subjects in corresponding categories. All possible categories as defined in the eCRF should be populated, even if they have zero counts. Percentages are based on the total number of subjects (N) for a given treatment and population, unless otherwise specified.

All summary tables will be presented by treatment group. Baseline summaries will also include a total summary column.

Individual subject data obtained from the eCRFs, external vendors, central clinical laboratory, central electrocardiogram (ECG) laboratory, and selected derived data will be presented by subject in data listings.

The analyses described in this plan are considered a priori, in that they have been defined before breaking the blind.

Any analyses performed after breaking the blind will be considered post hoc and exploratory. Post hoc analyses will be labeled as such on the output and identified in the CSR.

All analyses and tabulations will be performed using SAS® statistical software, version 9.4 or higher (SAS Institute Inc). TLFs will be presented in rich text format (RTF) and/or PDF.

The process for SAS program validation and quality control (QC) for programs and outputs is documented in the Synteract working instruction “SAS Programming Quality Control”. Study-specific QC requirements can be found in APPENDIX B: SAS PROGRAMMING QUALITY CONTROL REQUIREMENTS.

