12.2.9 Percentage of Subjects with a Decrease in Quantitative Mycobacterial Sputum

The ninth secondary efficacy endpoint is the percentage of subjects with a decrease in quantitative mycobacterial load from the sputum culture collected at the Day 84 visit and defined as a reduction in the semi-quantitative score (as defined in Table 10.3.2) as compared to baseline. The number and percentage of subjects with a reduction in the semi-quantitative score at the Day 84 visit will be presented for the ITT analysis set by treatment group. Exact 2-sided 95% CIs for the point estimate of the percentage of subjects with a decrease in each treatment group will be determined using the Clopper-Pearson method. The odds ratio (omadacycline relative to placebo) and p-value will be calculated using Cochran-Mantel-Haenszel test, stratified by prior antibiotic use. If the sample size is too small in one of the randomization stratification subgroups such that an adjusted analysis cannot be performed, an unadjusted analysis (chi-squared or Fisher's exact test) will be used.

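### The Day 84 sputum-load responder endpoint (SAP 12.2.9) is under an observed-data-only, no-ICE rule that conflicts with the SAP's full-N default and is an undeclared extension of the protocol

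*SAP*

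**What the plan says.** SAP 12.2 sets one rule for all secondary efficacy endpoints: "Missing data will not be imputed and no adjustment for ICEs will be performed". SAP 11.4 says of the same endpoints: "Summaries for these endpoints will be based on observed data only".

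SAP 12.2.9 defines the microbiological responder endpoint. The number and percentage with "a reduction in the semi-quantitative score at the Day 84 visit will be presented for the ITT analysis set", followed by Clopper-Pearson intervals and a CMH odds ratio and p-value stratified by prior antibiotic use. It says nothing about death, early stopping, a missing culture or alternative antibiotics. SAP 11.1 lists this endpoint at Day 84 only, whereas the visit-based PRO and global-impression endpoints are listed at both Day 84 and Day 84/EOT.

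SAP Section 6 gives a general default: "Percentages are based on the total number of subjects (N) for a given treatment and population, unless otherwise specified".

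Protocol 12.5.2.2 says the number and percentage with a decrease in load "will be determined by treatment group at Day 84 in the ITT Analysis Set". It gives no missing-data or rescue rule for this proportion. The protocol's available-data, no-substitution rule is in 12.5.2.1, which covers patient-reported outcomes and quality of life. SAP Section 14 declares no changes from the protocol's analyses.

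**The concern.** Having a Day 84 culture is a post-randomisation event. A subject who stops test article early goes to an EOT visit (Protocol 8.21), which SAP Section 7 defines separately from Day 84. If only subjects with a Day 84 culture are analysed, the odds ratio compares those who stayed, and randomisation no longer protects that comparison. An arm that loses more of its failures before Day 84 will look better microbiologically.

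This is the only microbiological secondary endpoint analysed as a response proportion at Day 84. Protocol 3.2 describes the study as the first trial to dose omadacycline beyond 14 days, so unequal early stopping against placebo cannot be ruled out in advance.

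The text also leaves room for two analysts to reach different results from the same data, because Sections 6 and 11.4 point to different denominators.

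**Working it through.** **Step 1. How each rule treats the same subject**

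Sources: SAP 12.1.1 and 12.1.2 (primary), 11.4 and 12.2 (literal reading), 6 (full N), 12.2.10 and 12.2.11 (time-to-event), and Protocol 8.10 (no sputum).

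| Subject | Primary endpoint | 12.2.9, literal 11.4 | 12.2.9, full N | 12.2.10–12.2.11, if no earlier event |
|---|---|---|---|---|
| Died before Day 84 | Non-responder (ICE-3) | Out | No decrease | Censored at death |
| Stopped early, EOT visit only, no rescue | Non-responder (ICE-4) | Out | No decrease | Censored if withdrawn from study |
| Rescued, EOT visit only | Non-responder (ICE-1) | Out | No decrease | Censored at rescue |
| Rescued, lower score in Day 84 window | Non-responder (ICE-1) | Success | Success | Censored at rescue |
| On treatment, attended Day 84, no sputum | Judged on symptoms | Out | No decrease | SAP silent |

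For the last row, Protocol 8.10 says inability to produce sputum after Baseline is a negative culture. That would score 0, which is a decrease from any positive baseline. The SAP does not carry this rule over.

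The time-to-event sections censor at death, withdrawal and rescue, so they depart from the blanket sentence in 12.2 under which they sit.

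**Step 2. The plan's own figure**

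SAP Section 5 claims "approximately 80% power to detect an absolute treatment difference of 30% in clinical response rate at Day 84", with 45 omadacycline and 30 placebo subjects, rates of 45% and 15%, and 2-sided alpha of 0.05.

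- Pooled rate: (45 × 0.45 + 30 × 0.15)/75 = 0.33
- Null SE: √[0.33 × 0.67 × (1/45 + 1/30)] = 0.1108
- Alternative SE: √[0.45 × 0.55/45 + 0.15 × 0.85/30] = 0.0987
- Power: Φ[(0.30 − 1.96 × 0.1108)/0.0987] = Φ(0.84) ≈ 79.9%

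Exact enumeration with an unstratified Mantel-Haenszel test gives 80.2%. The figure reproduces, but it concerns clinical response. The documents give no power, response rate or missing-data rate for the culture endpoint, so every count and rate below is assumed.

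**Step 3. Same data, two denominators**

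Assume 16 decreases on omadacycline with 9 of 45 cultures missing, and 5 on placebo with 3 of 30 missing.

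- Observed only: 16/36 = 44.4% vs 5/27 = 18.5%. OR = (16/20)/(5/22) = 3.52; unstratified Fisher p = 0.035.
- All randomised: 16/45 = 35.6% vs 5/30 = 16.7%. OR = (16/29)/(5/25) = 2.76; p = 0.115.

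A second assumed set, 20 of 36 vs 8 of 27 observed, gives OR (20/16)/(8/19) = 2.97. On all randomised it gives (20/25)/(8/22) = 2.20.

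**Step 4. Direction**

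Assume 45% vs 15% among subjects with a Day 84 culture, so the observed OR is 4.64. Multiply each rate by (1 − proportion missing) to count missing as no decrease.

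| Missing, omadacycline / placebo | Rates, all randomised | Difference (points) | OR |
|---|---|---|---|
| 10% / 10% | 40.5% vs 13.5% | 27.0 | 4.36 |
| 20% / 20% | 36.0% vs 12.0% | 24.0 | 4.13 |
| 30% / 30% | 31.5% vs 10.5% | 21.0 | 3.92 |
| 30% / 10% | 31.5% vs 13.5% | 18.0 | 2.95 |
| 10% / 30% | 40.5% vs 10.5% | 30.0 | 5.80 |

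If the observed rates are equal at 40%, counting missing as no decrease gives OR 0.69 with 30% vs 10% missing and 1.45 with 10% vs 30%.

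**Step 5. Post-rescue successes**

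Each one credited moves the all-randomised rate by 1/45 = 2.2 points on omadacycline or 1/30 = 3.3 points on placebo.

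**The case against.** The strongest reply is that Section 6 already settles the denominator. It uses the full N, 12.2 refers back to Section 6, and both 12.2 and 12.2.9 name the ITT set. On that reading nobody is dropped. This stands as a second reading, so exclusion is not established. It does not remove the problem. Section 6 allows exceptions and 11.4 reads like one. Keeping subjects without a culture in N as no decrease is in effect non-responder imputation, which 12.2 rules out. The CMH table also needs each subject classified or excluded, and 12.2.9 does not say which.

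Four stronger readings are tempting, and the documents do not support them:

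- **That the SAP reverses the protocol's ITT analysis.** Protocol 12.5.2.2 states no handling rule to reverse, and 12.2.9 repeats its population, visit, intervals and test.
- **That rescued subjects are routinely credited.** Those needing alternative therapy are to stop test article (Protocol 7.13) and go to EOT. A Day 84 culture after rescue should be limited to cases such as rescue close to Day 84, an unscheduled sample in the window, or rescue without stopping. The SAP does allow for it: 12.1.3 uses post-rescue Day 84 values in a sensitivity analysis.
- **That the sentence in 12.2 governs the 12.3 conversion counts.** SAP 11.1 lists those as additional, not secondary, endpoints. They have no stated missing-data or post-rescue rule.
- **That any missing culture is a failure.** Protocol 8.10 says otherwise for subjects who cannot produce sputum.

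Other outputs soften the consequence. SAP 12.3 has a score shift table that includes EOT and conversion at Day 84/EOT, and 12.2.11 gives Kaplan-Meier probabilities of a negative culture. Efficacy is exploratory with nominal p-values, so no error-rate claim is affected. A secondary endpoint may also use a different strategy from the primary, provided it is stated and consistent.

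**Conclusion.** The point holds as an internal conflict in the SAP plus an undeclared extension. Read literally, 11.4 and 12.2 make the 12.2.9 comparison conditional on having a Day 84 culture and leave post-rescue cultures eligible as successes. That conflicts with the Section 6 default and differs from the primary endpoint's composite rule. The blanket sentence is itself contradicted by 12.2.10 and 12.2.11. The protocol's no-substitution rule for patient-reported outcomes has been carried over to microbiology, and Section 14 does not say so.

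The size is unknown. The illustrations show that the choice of denominator can move the odds ratio materially (3.52 to 2.76 in one assumed set) and in either direction. They do not show that it will, or that it favours omadacycline. The conclusion rests on early stoppers usually lacking a Day 84 culture, which follows from the visit definitions but whose frequency the documents do not give. The SAP should be changed; the primary analysis is unaffected.

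**What to change.** In SAP 12.2.9:

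- Use all ITT subjects as the denominator.
- Count a subject with ICE-1, ICE-3, ICE-4 or a missing Day 84 culture as no decrease.
- Make one exception. A subject without one of these ICEs who attended but could not produce sputum after reasonable attempts is culture-negative, as Protocol 8.10 requires. Write that rule into the SAP.
- Do not credit a culture collected on or after the start of alternative NTM antibiotics (chronic macrolides excluded, as in ICE-1).
- Keep the observed-case analysis as sensitivity.

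Elsewhere: state the same denominator and post-rescue rule for the conversion proportions in 12.3, exempt 12.2.9 to 12.2.11 from the blanket sentences in 12.2 and 11.4, and list the choice in Section 14.

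The cost is SAP wording and reuse of the ICE flags already needed for the primary endpoint. Response rates will generally be lower. Counting missing as no decrease is not neutral either: it can shift the odds ratio either way when missingness differs between arms (Step 4), which is why the observed-case table should stay beside it.

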12.5.2 Secondary Efficacy Endpoints

12.5.2.1 Patient-Reported Outcomes and Quality of Life

For each patient-reported outcome and quality of life endpoint, analyses will be conducted in the ITT Analysis Set. Available data will be used; there will be no substitutions for missing data.

The QOL-B includes domains for physical functioning, role functioning, vitality, emotional functioning, social functioning, treatment burden, health perceptions and respiratory symptoms. For each domain, scores will be standardized on a 0 to 100 scale. Descriptive statistics for each domain at baseline and each visit will be presented by treatment group. The change from baseline to each visit will be analyzed using an analysis of covariance (ANCOVA) and the least squares (LS) mean, standard error (SE) of the LS mean and 2-sided 95% CI for the LS mean will be provided for each treatment group. The difference in LS means between treatment groups, 2-sided 95% CI and p-value will also be provided.

For the SGRQ, the global score and score for each component (symptoms, activity, and impacts) will be determined. Descriptive statistics for the global score and each component score at each visit will be presented by treatment group. The change from baseline to each visit will be analyzed using an ANCOVA, and the LS mean, and 2-sided 95% CI for the LS mean will be provided for each treatment group. The difference in LS means between treatment groups, 2-sided 95% CI and p-value will also be provided.

For the PROMIS Fatigue 7a Short Form, raw scores are converted to a standardized score. Descriptive statistics for the standardized score at baseline and each visit will be presented by treatment group. The change from baseline to each visit will be analyzed using an ANCOVA, and the LS mean, SE of the LS mean, and 95% CI for the LS mean will be provided for each treatment group. The difference in LS means between treatment groups, 95% CI and p-value will also be provided.

For the PGI-S, the number and percentage of subjects with each response will be presented by visit and treatment group. The PGI-S will also be categorized as mild/not present vs. moderate/severe and the number and percentage of subjects in each category will be presented by visit and treatment group. Exact 2-sided 95% CIs using the Clopper-Pearson method for the percent improved and a p-value from Fisher's exact test will be provided.

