12.2.1 Quality of Life – Bronchiectasis (QOL-B)

The first secondary efficacy endpoint is the change from baseline in the QOL-B domain scores at the Days 28, 56, and 84 visit, and Day 84/EOT. Descriptive statistics will be provided for each domain at each time point and ANCOVA estimates will be provided as described in [Section 12.2](#). A graph of the cumulative distribution of the change from baseline to Day 84 for the respiratory domain by treatment group will also be provided.

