12.2.2 St George's Respiratory Questionnaire (SGRQ)

The second secondary efficacy endpoint is the change from baseline in the SGRQ global and component scores at the Day 28, 56, and 84 visit, and Day 84/EOT. Descriptive statistics will be provided for the global score and each component score at each time point and ANCOVA estimates will be provided as described in [Section 12.2](#).

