12.2.3 Patient-reported Outcomes Measurement Information System (PROMIS)

The third secondary efficacy endpoint is the change from baseline in the PROMIS Fatigue 7a Short Form standardized score at the Day 28, 56, and 84 visit, and Day 84/EOT. Descriptive statistics will be provided for the standardized score at each time point and ANCOVA estimates will be provided as described in [Section 12.2](#).

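### The Day 84 comparisons of QOL-B, SGRQ and PROMIS Fatigue use observed cases visit by visit, and are biased if symptom-related dropout differs between arms

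*SAP*

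**What the plan says.** SAP 12.2 sets the model: where appropriate, secondary endpoints "will be analyzed using an analysis of covariance (ANCOVA) model at each visit which will include the change from baseline as the dependent variable". Treatment and prior-antibiotic stratum are factors, and the baseline score is a covariate. Sections 12.2.1 (QOL-B domains), 12.2.2 (SGRQ) and 12.2.3 (PROMIS Fatigue) all refer back to it. For SGRQ, for example: "Descriptive statistics will be provided for the global score and each component score at each time point and ANCOVA estimates will be provided".

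Three places fix the handling of missing values:
- SAP 12.2: "Missing data will not be imputed and no adjustment for ICEs will be performed".
- SAP 11.4: "Summaries for these endpoints will be based on observed data only".
- Protocol 12.5.2.1, which also names ANCOVA: "Available data will be used; there will be no substitutions for missing data".

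The scales are collected at baseline and Days 28, 56 and 84 (Protocol Appendix 1). The SAP reports both a Day 84 row and a Day 84/EOT row. The second adds the end-of-treatment value of subjects who stopped early. No repeated-measures model, imputation or missing-data sensitivity analysis is specified for these scales.

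**The concern.** The Day 84 model contains only subjects with a Day 84 score. For everyone else, the Day 28 and Day 56 scores feed their own visit models but do not inform the Day 84 estimate.

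The protocol gives a reason to expect that these subjects are not a random subset. Under Protocol 7.13 and 8.19.5, a subject whose disease worsens enough to need other antibiotics stops test article. Protocol 8.21 then asks for an EOT visit and a safety follow-up, if possible; it does not ask for the remaining scheduled questionnaires. The scales measure symptoms, function and fatigue, so earlier scores plausibly predict who is missing. In a placebo-controlled antibiotic trial, that link may differ by arm. What is at stake is the size of the Day 84 treatment difference on scales meant to support the first assessment of efficacy.

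**Working it through.** **1. The plan's own figure.** The only sample-size figure is for the primary endpoint (SAP 5): 45 vs 30 subjects, 45% vs 15%, 2-sided 0.05. The pooled rate is (45 × 0.45 + 30 × 0.15)/75 = 0.33. The null SE is √(0.33 × 0.67 × (1/45 + 1/30)) = 0.1108, and the alternative SE is √(0.45 × 0.55/45 + 0.15 × 0.85/30) = 0.0987. Then z = (0.30 − 1.96 × 0.1108)/0.0987 = 0.84, so power is 79.9%. The stated 80% reproduces. It says nothing about the questionnaire scales, for which no SD, correlation or dropout rate is given. Everything below rests on assumed values.

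**2. When the Day 84 ANCOVA is right.** In each arm, let the shift be the observed-case LS mean minus the true mean. Then

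bias of the difference = drug shift − placebo shift.

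This is zero if, given arm, baseline and stratum, missingness is unrelated to the Day 84 score, or if the two shifts cancel. Two checks against a true difference of 8 show that the dropout rate alone is not the criterion:
- Dropout driven only by baseline score, 9% vs 27% missing: the estimate was 7.99, because baseline is in the model.
- Similar rates (23% vs 20%) but opposite dependence on post-baseline score: the estimate was 6.35.

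**3. Simulation in SD units.** Inputs (all assumed): SD 1, equal correlation 0.6, 60:40 allocation, higher score better, and a true difference rising in equal steps to 0.50 at Day 84. Dropout after Day 28 and after Day 56 has logit a − b × (change from baseline). In (a), a = −2.5 and b = 1.5 in both arms. In (b), b = 0 on drug. In (c), placebo has a = −1.8 and b = 2, and drug is as in (b). There were 400,000 simulated subjects per pattern.

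| Pattern | Missing drug / placebo | Drug shift | Placebo shift | Bias | Day 84 ANCOVA | Last/EOT value | All-visit model |
|---|---|---|---|---|---|---|---|
| (a) same rule in both arms | 18% / 23% | +0.058 | +0.076 | −0.018 | 0.48 | 0.47 | 0.50 |
| (b) symptom-driven on placebo only | 15% / 23% | +0.002 | +0.072 | −0.070 | 0.43 | 0.57 | 0.50 |
| (c) stronger on placebo | 15% / 39% | 0.000 | +0.139 | −0.139 | 0.36 | 0.63 | 0.50 |

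The all-visit model is sequential regression under missing at random, which stands in for an MMRM. The last-value column approximates the Day 84/EOT row. It does not recover 0.50 either, and in (b) and (c) it errs in the opposite direction.

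At N = 75, the root mean square error (ANCOVA vs all-visit) was 0.217 vs 0.215 in (a), 0.220 vs 0.208 in (b) and 0.268 vs 0.231 in (c).

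**4. The same question in points.** Assumed: N = 75, SD 18, correlation 0.7, true difference 8. Ranges come from two variants of the simulation.

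| Missing drug / placebo | Bias of Day 84 ANCOVA | As share of 8 |
|---|---|---|
| Common rule in both arms | about −0.2 | −2.5% |
| About 8% / 36% | −1.6 to −2.9 | −20% to −36% |
| About 28% / 13% | +1.2 to +2.2 | +15% to +28% |

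The repeated-measures estimate was about 8.0 in both unequal patterns. Rescaling step 3 gives similar sizes: −0.018 × 18 = −0.3, −0.070 × 18 = −1.3 and −0.139 × 18 = −2.5. In head counts, 8% / 36% is about 4 of 45 and 11 of 30 subjects.

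**5. Precision.** The variance ratio (ANCOVA over repeated measures) was 1.02 to 1.06 in step 4. In step 3 the standard deviations at N = 75 give (0.216/0.215)² = 1.01, (0.209/0.208)² = 1.01 and (0.229/0.231)² = 0.98.

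**The case against.** **The plan already provides for discontinuers.** The Day 84/EOT row brings in EOT values, and Protocol 8.21 asks for that visit. This stands as a description: a reader might infer that discontinuers vanish from the analysis, or that Day 28 and Day 56 scores are discarded, and neither is true. But the row combines scores from different study days, so it answers a different question, and step 3 shows that it need not be nearer the Day 84 truth.

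**The unequal patterns are assumed.** This stands. Inclusion criterion 4 requires that guideline antibiotics are not expected to be needed within 3 months, and cavitary disease is excluded. Both argue against taking heavy placebo loss for granted. Under a common rule the bias is small: about −0.2 with equal correlation, and up to about −0.6 in a separate simulation whose correlation decayed over time.

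**An MMRM is not assumption-free.** This stands. It assumes missing at random. If it projects beyond discontinuation from on-treatment scores, it leans towards the effect had subjects continued, whereas the SAP presents scores as collected.

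**The endpoints are exploratory.** This stands and limits the weight of the point. P-values are nominal, there is no multiplicity control, and per-visit ANCOVA agrees with the protocol. It does not justify leaving collected data out of the Day 84 estimate when a standard model can use them.

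**Conclusion.** The point holds, with limits. The planned Day 84 comparisons on these scales are exposed to bias if dropout depends on post-baseline scores differently in the two arms, and the protocol contains a route by which that could happen. The bias can go either way. On the stated assumptions it runs from about −2.9 to +2.2 against a true difference of 8, and is near zero under a common dropout rule. These figures illustrate the risk; they neither predict nor bound it, because the documents supply none of the inputs.

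Stronger readings are not supported:
- Unequal dropout does not by itself bias the estimate, and equal dropout does not by itself protect it (step 2).
- A repeated-measures model is not worth having mainly for precision; the variance gain is at most about 2 to 6%.
- The primary result is not affected. Clinical response counts a missing Day 84 assessment as non-response (SAP 12.1.1 and 12.1.2).

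This is a recommended improvement to secondary, exploratory analyses.

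**What to change.** For each QOL-B domain, the SGRQ global and component scores, and the PROMIS Fatigue score, fit one MMRM for change from baseline. Include treatment, visit, treatment-by-visit, baseline, baseline-by-visit and prior-antibiotic stratum, with unstructured covariance and Kenward-Roger degrees of freedom. Report the treatment contrast at Days 28, 56 and 84. Keep the per-visit ANCOVA and the Day 84/EOT row as sensitivity analyses.

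State the estimand: whether scores after discontinuation of test article or after alternative antibiotics are included. Also say how an EOT score that falls outside a scheduled visit window enters the model.

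Protocol 12.5.2.1 names ANCOVA and SAP Section 14 currently declares no changes, so record the departure there before unblinding. Under SAP Section 6, an analysis performed after the blind is broken is post hoc unless it was defined beforehand.

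The cost is SAP text, a documented departure from the protocol and standard programming; no new data are needed. The downside is reliance on missing at random: the model corrects only for dropout explained by observed scores.
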